6.2. Secondary Efficacy Endpoints

- Subject symptom relief via VCSS pain score at 12 months
- Primary assisted patency at 12 months
 - Defined as freedom from DUS core laboratory adjudicated occlusion or stenosis $>50\%$ within the stented segment following a reintervention due to a $>50\%$ but $<100\%$ stenosis. If DUS shows $>50\%$ stenosis or occlusion, confirmation by diagnostic IVUS is required.
- Secondary patency at 12 months
 - Defined as freedom from DUS core laboratory adjudicated occlusion or stenosis $>50\%$ within the stented segment following a reintervention due to 100% occlusion. If DUS shows $>50\%$ stenosis or occlusion, confirmation by diagnostic IVUS is required.

6.3. Observational Endpoints

- Device Success defined as:
 - Successful deployment of the DUO stent(s) at the intended target site, AND
 - Successful withdrawal of the delivery catheter(s) from the introducer sheath, AND
 - The DUO Stent remaining at the intended deployment location through completion of the index procedure as determined by the Principal Investigator (PI)
- Lesion success defined as target lesion patency of $\leq 50\%$ residual diameter or area stenosis of the stented segment at the completion of the procedure*
- Procedural success defined as lesion success without the occurrence of CEC adjudicated major adverse events (MAEs) from the time start of the index procedure through discharge*
- Stent fracture via X-ray through 36 months*
- Stent migration via X-ray through 36 months*
- Stent embolization via X-ray or venogram through 36 months*
- Primary patency of the stented segment via DUS at 24 and 36 months. If DUS shows $>50\%$ stenosis or occlusion, confirmation by diagnostic IVUS may be required.*
- Primary assisted patency of the stented segment via DUS at 24 and 36 months. If DUS shows $>50\%$ stenosis or occlusion, confirmation by diagnostic IVUS may be required.*
- Secondary patency of the stented segment via DUS at 24 and 36 months. If DUS shows $>50\%$ stenosis or occlusion, confirmation by diagnostic IVUS may be required.*
- Changes in the clinical CEAP Classification through 36 months
- Changes in the EQ-5D-3L through 36 months
- Changes in the Villalta Score through 36 months
- Changes in the VCSS Pain Score at 24 and 36 months
- Changes in the VEINES QOL/Sym Score through 36 months
- CEC adjudicated MAEs post 30 days through 36 months
- CEC adjudicated CD-TLR through 36 months
- CEC adjudicated CD-TVR through 36 months
- Venous Ulcer Assessment through 36 months

*Core Laboratory adjudicated

7. CLINICAL TRIAL DESIGN

This is a prospective, multi-center, single-arm, non-blinded clinical trial designed to investigate the safety and efficacy of the Vesper DUO Venous Stent System as compared to a pre-defined performance goal (PG) established from published, peer reviewed scientific literature related to stenting of iliofemoral venous outflow obstructions.

7.1. Anticipated Number of Subjects and Investigational Sites

Up to 160 subjects will be enrolled at up to 45 U.S. and International investigative sites. Each site can enroll a maximum of 32 subjects, establishing an enrollment cap at 20% of the total subject sample size.

7.2. Subject Population

Subjects with nonmalignant iliofemoral venous outflow obstruction presenting with nonthrombotic (NT), acute thrombotic (AT), or chronic postthrombotic (CPT) disease pathogenesis will be selected for study participation. At least 20% of the total population must be enrolled in each group. Subjects must meet all inclusion criteria and not meet any of the exclusion criteria to be enrolled in this clinical trial.

7.3. Clinical Trial Duration & Follow-up

The follow-up duration for each enrolled subject who receives a DUO Stent implant is 36 months. Any subject who is enrolled but does not receive at least one DUO Stent implant will be followed for 30 days and then exited from the study (see **Section 13.3.1**).

7.4. Subject Selection

7.4.1. Inclusion Criteria

Subjects must meet all the following Inclusion Criteria. The response for each criterion below must be “Yes”:

1. Males or non-pregnant, non-breastfeeding females ≥ 18 years of age at the time of consent
2. Subject is able and willing to provide written informed consent prior to receiving any non-standard of care, protocol specific procedures
3. Female subjects of childbearing potential must have a negative pregnancy test within 7 days prior to treatment and must use some form of contraception (abstinence is acceptable) throughout the time of clinical trial exit
4. Willing and capable of complying with all required follow-up visits
5. Estimated life expectancy ≥ 1 year
6. Subject is ambulatory (use of assistive walking device such as a cane or walker is acceptable)
7. Body mass index (BMI) < 45

8. Clinically significant symptomatic venous outflow obstruction in one iliofemoral venous segment (one limb) per subject, is indicated for venoplasty and stenting, and meets at least one of the following clinical indicators:
 - a. CEAP score ≥ 3
 - b. VCSS pain score ≥ 2
 - c. Suspected deep vein thrombosis (DVT) with symptoms occurring prior to receiving a DUO Stent
9. Subject is willing and able to comply with PI recommendation for compression therapy, if required
10. Presence of unilateral, non-malignant venous obstruction of the common femoral vein (CFV), external iliac vein (EIV), common iliac vein (CIV), or any combination thereof, defined as a $\geq 50\%$ reduction in target vessel lumen diameter and confirmed by venographic or IVUS imaging. The cranial point of the obstruction may extend to the iliac vein confluence of the inferior vena cava (IVC) and the caudal point may be 2mm above either the inflow of the deep femoral (or profunda) or the lesser trochanter, whichever is most cranial
11. Obstructive lesion(s) able to be treated with continuous stent coverage
12. Adequate inflow to the target lesion(s) involving at least a patent femoral or deep femoral vein and a landing zone in the CFV free from significant disease requiring treatment
13. Reference vessel diameter is of adequate size to accommodate the appropriate size stent as measured by IVUS
14. All vessels from insertion site through target vessel can accommodate a 9F or 10F sheath, depending on the stent size used
15. Ability to cross interventional devices through target lesion(s)
16. In DVT subjects, successful treatment of acute thrombus must have occurred prior to receiving any DUO Stents for an underlying obstructive lesion. Successful treatment of acute thrombus is defined as reestablishment of antegrade flow with $\leq 30\%$ residual thrombus (confirmed by venogram or IVUS) and freedom from bleeding and symptomatic pulmonary embolism (confirmed by imaging). After successful treatment of thrombus is confirmed, eligible obstructive lesion(s) can be treated with a DUO Stent during the same procedure.
17. All subjects must undergo a SARS-CoV-2 test and have a negative test result within 8 days prior to the index procedure. If a SARS-CoV-2 test is unavailable due to institution policy, a test shortage, or if there is a delay in test results, the subject must complete the COVID-19 questionnaire and must have answered NO to all questions to be eligible for enrollment. A SARS-CoV-2 test will not be required for enrollment if a subject has received a complete cycle of an authorized COVID-19 vaccine or has documented evidence of a positive COVID-

- 19 antibody test and is asymptomatic and has no long-lasting effects (per PI discretion) from a prior COVID-19 infection.
18. A measured temperature less than 99.5°F (37.5°C) on the day of the index procedure and no history of fever or feeling feverish within 14 days of the index procedure
19. No prior history, within 60 days of the index procedure, of a SARS-CoV-2 positive test, or COVID-19 symptoms

7.4.2. Exclusion Criteria

Subjects must not meet any of the following Exclusion Criteria. The response for each criterion below must be “No”:

1. Target limb symptoms caused by peripheral arterial disease
2. Presence of unresolved significant pulmonary emboli prior to use of the DUO Venous Stent System confirmed by chest CT. If subject has documented history of significant pulmonary embolism within the last 6 months, a chest CT is required to confirm significant pulmonary embolism is not currently present.
3. Presence of IVC obstruction or target venous obstruction that extends into the IVC
4. Presence of acute DVT located outside target limb
5. Contralateral venous occlusive disease of the CFV, EIV, and/or CIV, with planned treatment ≤ 390 days after the index procedure
6. Uncontrolled or active coagulopathy or known, uncorrectable bleeding diathesis
7. Coagulopathy causing INR >2 which is not amenable to medical treatment
8. Platelet count $<50,000$ cells/mm³ or $>1,000,000$ cells/mm³ and/or White blood cell (WBC) $<3,000$ cells/mm³ or $>12,500$ cells/mm³
9. Uncorrected hemoglobin of ≤ 9 g/dL
10. Subject is on dialysis or has an estimated glomerular filtration rate (eGFR) <30 mL/min. In subjects with diabetes mellitus, eGFR <45 mL/min.
11. History of Heparin Induced Thrombocytopenia
12. Presence of known aggressive clotting disorders such as Lupus Anticoagulant Disorder, Antiphospholipid antibody syndrome, homozygous gene Factor V Leiden or Prothrombin gene abnormalities, Protein C and S deficiency or Antithrombin deficiency
13. Known hypersensitivity or contraindication to antiplatelet therapy or anticoagulation, nickel, or titanium
14. Contrast agent allergy that cannot be managed adequately with pre-medication

15. Intended concurrent adjuvant procedure (except for venoplasty) such as creation of temporary arteriovenous fistula, femoral endovenectomy or saphenous vein ablation and/or saphenous vein stripping during the index procedure
16. Subjects who have had any prior surgical or endovascular procedures to the target vessel. Note that subjects who have had successful catheter-directed or mechanical thrombolysis in the target vessel for DVT at least 90 days prior to the index procedure may be included
17. Planned surgical or interventional procedures of the target limb (except thrombolysis and/or thrombectomy in preparation for the procedure or vena cava filter placement prior to stent implantation in subjects at high risk for pulmonary embolism) within 30 days prior to or 30 days after the index procedure
18. Planned surgical or interventional procedures for other medical conditions (i.e., not associated with the target limb) 30 days prior to or 30 days after the index procedure
19. Previous venous stenting of the target limb, the IVC, or contralateral limb if stents extend into the IVC
20. Iliofemoral venous segment unsuitable for treatment with available sizes of DUO Stent implants
21. Lesions with intended treatment lengths extending into the IVC
22. No safe landing zone at or above the profunda femoral confluence
23. Participating in another investigational study in which the subject has not completed the primary endpoint(s)
24. Has other comorbidities that, in the opinion of the PI, would preclude them from receiving this treatment and/or participating in study-required follow-up assessments

8. TREATMENT PLAN

8.1. Time and Events Schedule

All subjects will receive the assessments at specific time points as listed below:

Assessment	Baseline ¹	Index Procedure	Post-Procedure/ Pre-Discharge *	30-day (-2 days/+14 Days) ¹⁴	6 Month (±30 Days) ¹⁴	12 Month (± 30 Days) ¹⁴	24 Month (± 30 Days) ¹⁴	36 Month (± 30 Days) ¹⁴	Unscheduled ^{9,10}
Informed Consent	X ²								
Inclusion/Exclusion Criteria	X	X							
SARS-CoV-2 Test/COVID- 19 Questionnaire ⁴	X ³			X	X	X	X	X	X
Demographics, Medical History and Risk Factors	X								
Brief Physical Exam (Height, Weight, Temp)	X								
Serum Creatinine, eGFR, WBC, Platelet Count, Hemoglobin	X								
Prothrombin Time (PT)/ International Normalized Ratio (INR) ⁵	X		X						
Activated Partial Thromboplastin time (aPTT) ⁶	X		X						
Urine or Blood Pregnancy Test ⁷	X								
Venous Ulcer Assessment	X			X	X	X	X	X	X
CEAP Classification	X				X	X	X	X	X
Villalta Score	X				X	X	X	X	X
VCSS Pain Score	X				X	X	X	X	X
VEINES-QOL/Sym Questionnaire	X				X	X	X	X	X
EQ-5D-3L Questionnaire	X				X	X	X	X	X
Concomitant Medications	X	X	X	X	X	X	X	X	X
Duplex Ultrasound (DUS) ^{8,11}				X	X	X	X	X	X
Venogram ¹¹		X ¹⁵				X ¹²	X ¹⁶	X ¹⁶	X
Intravascular Ultrasound (IVUS) ¹¹		X ¹⁵				X ¹²	X ¹⁶	X ¹⁶	X
X-ray of Implanted Stent ¹¹						X	X	X	X

Adverse Event (AE) Assessment ¹³		X	X	X	X	X	X	X	X
---	--	---	---	---	---	---	---	---	---

* Assessments are to be completed post-index procedure and prior to the subject being discharged from the hospital/clinic.

¹ Assessments may be done up to 30 days prior to the index procedure, except for a pregnancy test and SARS-CoV-2 test

² Informed Consent may be obtained up to 30 days prior to index procedure.

³ All subjects must undergo a SARS-CoV-2 test and have a negative result within 8 days of the Index Procedure to be eligible for study inclusion. COVID-19 questionnaire is only required under certain circumstances when SARS-CoV-2 testing is not possible.

⁴ If a SARS-CoV-2 test is unavailable due to institution policy, a test shortage, or if there is a delay in test results, the subject must complete the COVID-19 questionnaire and answer NO to all questions to be eligible for study treatment. If a SARS-CoV-2 test is unavailable due to institution policy or a test shortage at the time of any follow-up or unscheduled visits, the COVID-19 questionnaire must be completed. A SARS-CoV-2 test will not be required if a subject has received a complete cycle of an authorized COVID-19 vaccine or has documented evidence of a positive COVID-19 antibody test, is asymptomatic, and has no long-lasting effects (per PI discretion) from a prior COVID-19 infection.

⁵ PT/INR to be obtained only if a subject is on chronic warfarin therapy.

⁶ aPTT to be obtained only if a subject is on chronic heparin therapy.

⁷ Negative urine or blood pregnancy test is required for female subjects of childbearing potential within 7 days of the index procedure.

⁸ All scheduled DUS exams should be performed per the protocol established by the core laboratory. If a DUS is non-diagnostic (per the imaging protocol), the site should make every effort to obtain a repeat exam within the visit window.

⁹ Unscheduled tests and assessments should be completed prior to any interventional procedures to target limb.

¹⁰ Unscheduled tests and assessments to be performed as clinically indicated.

¹¹ All imaging of the target limb acquired during scheduled visits or an interventional procedure to the target limb (such as venogram, IVUS, DUS, or X-ray) should be submitted to the respective core laboratory within 3 business days.

¹² Required if DUS suggests >50% stenosis or occlusion of the stented segment, or if the DUS is non-diagnostic or sub-optimal (i.e., due to obesity). If a follow-up venogram and/or IVUS is refused by the subject, this must be documented and will not be considered a protocol deviation.

¹³ For the purposes of this study, all AEs, regardless of relatedness to the study device and/or study device procedure, target limb, or underlying venous disease are required to be reported on the AE eCRF and are considered “protocol reportable”. Please see **Section 17** for more information on safety events and reporting requirements.

¹⁴ Follow-up assessments (required at the 30-day visit and beyond) that cannot be performed due to a subject’s medical condition (i.e., amputation) will not be considered protocol deviations if documentation of the medical condition is present in the subject’s medical records.

¹⁵ To be performed both pre-and post-study device treatment as outlined in **Sections 9.5** and **9.6** and as described in the core laboratory manuals.

¹⁶ May be required if DUS suggests >50% restenosis or occlusion of the stented segment **and** if the subject is presently symptomatic requiring a reintervention. If a follow-up venogram and/or IVUS is refused by the subject, this must be documented and will not be considered a protocol deviation.

9. REQUIRED TESTS AND ASSESSMENTS

The tests and assessments described in this section are required at baseline and/or at various follow-up visits according to the Time and Events Schedule in **Section 8.1**.

9.1. Laboratory Testing

Laboratory blood samples must be drawn pre-procedure but may not exceed 30 days prior to the index procedure.

Laboratory samples include:

- Serum Creatinine, eGFR, WBC, Platelet Count, Hemoglobin
- PT/INR (only if a subject is on chronic warfarin)
- aPTT (only if a subject is on chronic heparin)
- Pregnancy test (if female of childbearing potential) within 7 days prior to index procedure
- SARS-CoV-2 test and/or COVID-19 questionnaire within 8 days prior to index procedure (not required if subject has received a COVID-19 vaccination or shows positive for COVID-19 antibodies per Inclusion 17)

9.2. SARS-CoV-2 Testing

It is required that all subjects undergo testing for the Severe Acute Respiratory Syndrome Coronavirus 2 (SARS-CoV-2) that results in the Coronavirus Disease 2019 (COVID-19) within 8 days prior to the index procedure. The result of this test must be negative for the subject to be eligible for enrollment in this clinical trial. If the test is positive, the subject must be documented as a screen failure.

A SARS-CoV-2 test will not be required if a subject has received a complete cycle of an authorized COVID-19 vaccine or has documented evidence of a positive COVID-19 antibody test and is asymptomatic and has no long-lasting effects from a prior COVID-19 infection.

If a SARS-CoV-2 test is unavailable due to institution policy, a test shortage, or if there is a delay in test results, the subject must complete the COVID-19 questionnaire. If the subject answers NO to all questions on the questionnaire and meets all other inclusion/exclusion criteria, the subject may be enrolled in this clinical trial. In the event that a subject is enrolled in this clinical trial without a SARS-CoV-2 test, the reason must be documented in the subject's study records and be able to be verified by the Sponsor in order to avoid a protocol deviation.

All enrolled subjects that receive a DUO Venous Stent(s) must undergo a SARS-CoV-2 test at every follow-up visit as well as all unscheduled visits. If at any time a SARS-CoV-2 test is unavailable, the COVID-19 questionnaire must be administered. If the results of this test are positive at any time throughout the duration of the clinical trial, this must be documented as an adverse event. If at any time a subject does test positive, no further SARS-CoV-2 testing is required. Please see **Section 17** for more information on safety events and reporting requirements.

A SARS-CoV-2 test will not be required at follow-up if one of the following have occurred:

1. Subject was enrolled under the vaccination and/or antibody requirements for Inclusion 17
2. Subject has received a full cycle of an authorized COVID-19 vaccination
3. Subject has documented evidence of a positive COVID-19 antibody test and is asymptomatic and has no long-lasting effects from a prior COVID-19 infection

9.3. **Clinical Assessments**

9.3.1. **Venous Disease State Classification**

Subjects will be grouped and analyzed based on their pre-treatment disease etiology. The PI will determine Venous Disease State Classification by classifying the subject as nonthrombotic, acute thrombotic, or chronic postthrombotic based on the criteria outlined below. The Venous Disease State Classification will be documented accordingly in the subject's source records and in EDC.

1. Nonthrombotic group:

- Symptomatic subjects with iliofemoral venous obstruction and no history of DVT
- If complete obstruction/occlusion extends into the EIV or CFV without involvement of iliac veins, subject should be classified as chronic postthrombotic

2. Acute thrombotic group:

- First episode of acute symptomatic ipsilateral DVT \leq 14 days old with venographic or IVUS evidence of acute clot and iliofemoral obstruction requiring stent placement
- Successful clot removal required prior to stent placement
- Prior to stent placement, if target lesion shows evidence of a chronic component, subject will be classified as chronic postthrombotic

3. Chronic postthrombotic group:

- Total occlusion or stenosis of iliofemoral segments requiring stent placement with onset of symptoms more than 14 days ago
- Any obstruction of iliofemoral segments with history of ipsilateral DVT within 2 years regardless of onset of symptoms

9.3.2. **Venous Ulcer Assessment**

An assessment of existing and/or new venous ulcers is to be performed according to the Time and Events Schedule in **Section 8.1**. Any pre-existing venous ulcers documented at Baseline will be followed until they are resolved or until the subject completes/is exited from the study. Any new venous ulcers that develop during follow-up will be documented and followed in the same manner. For all documented venous ulcers, the PI or Sub-Investigator (Sub-I) will classify them as Healed, Improving, Unchanged, or Worsening as well as the location of each. If, at the time of any follow-up visit, a subject’s venous ulcer is dressed and it is not advisable to remove the dressing per PI discretion, this should be clearly documented and will not be considered a protocol deviation.

9.3.3. **Clinical-Etiology-Anatomy-Pathophysiology (CEAP) Classification**

The Clinical aspect of the CEAP classification will be used to categorize venous disease. The ‘Clinical’ signs of venous disease are those that are visible and used to categorize the subject from C0 to C6.

Clinical CEAP Classification	
Clinical Classification	Description
C0	No visible or palpable signs of venous disease
C1	Telangiectasia or reticular veins
C2	Varicose veins
C2r	Recurrent varicose veins
C3	Edema
C4	Changes in skin and subcutaneous tissue secondary to chronic venous disease
C4a	Pigmentation or eczema
C4b	Lipodermatosclerosis or atrophie blanche
C4c	Corona phlebectatica
C5	Healed
C6	Active venous ulcer
C6r	Recurrent active venous ulcer

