19.11. Primary Efficacy Objective

Subjects Included the Analysis: Subjects who meet the ITT definition.

Efficacy: Primary patency of stented segment (confirmed by core laboratory) at 12 months evaluated per subject.

Hypothesis:

H_0 : Proportion of subjects with primary patency (p_{p_pat}) is less than or equal to performance goal (PG) at 12 months, $p_{p_pat} \leq PG$

H_1 : Proportion of subjects with primary patency is greater than the performance goal at 12 months, $p_{p_pat} > PG$

The primary patency proportion will be calculated such that the numerator is the number of subjects found to be patent at 12 months. The denominator is the total number of subjects found to be patent or not patent at 12 months.

Patency is:

- An in-window patent stenosis assessment with no reintervention per definition prior to the close of the 12-month window.
- In the absence of an in-window stenosis assessment, a subsequent patent stenosis assessment with no prior reintervention per definition can be used to declare patency at 12 months.

Lack of patency is:

- A reintervention per definition prior to the close of the 12-month visit window.
- A non-patent stenosis assessment within the 12-month visit window.

Performance Goal: The PG for primary efficacy will be set when all enrolled subjects complete the index procedure of this pivotal IDE trial based upon the proportions of ITT subjects in each of the disease states, i.e. nonthrombotic (p_{NT_ENROLL}), acute thrombotic (p_{AT_ENROLL}) and chronic postthrombotic (p_{CPT_ENROLL}). The disease state specific PGs were adopted as suggested in Razavi et al¹ that is, the lower 95% confidence limit minus 0.10. The disease state PGs are .83, .70 and .66 for nonthrombotic, acute thrombotic and chronic postthrombotic subjects respectively. The PG for the

pivotal study will be a weighted combination of these disease state specific PGs, where the weights are the proportion of subjects in each disease state in the ITT sample, i.e. study PG = $(p_{NT_ENROLL}) * 0.83 + (p_{AT_ENROLL}) * .70 + (p_{CPT_ENROLL}) * 0.66$. The same PG will be used overall and in the SARS-CoV-2 negative subgroup. In order to have a minimum number of subjects from each disease condition in the ITT sample, the study will require that at least 20% of the ITT subjects are in each of the disease state.

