Sample Size Rationale: With an expected FAS sample size of N=128, one-sided Type I error less than or equal to 2.5%, and assumed primary patency at 12 months equal to .96, .87, .79, i.e. the point estimates for primary patency from Razavi et al for nonthrombotic, acute thrombotic, and chronic postthrombotic respectively, the power for primary efficacy ranges from 96 – 99% depending on proportion in each disease-state given a minimum of at least 20% in each group. The table below provides the matrix of simulated power varying the ITT proportions for the disease states.

Power Calculations Using Simulation for the Primary Statistical Analysis

Proportion of Subjects Expected in Each Group			Assumed Freedom from Primary Efficacy				Calculated Performance Goal				Power at N=128 Evaluable (20% attrition for N=160 enrolled)
NT	AT	CPT	NT	AT	CPT	Pooled	NT	AT	CPT	PG	One-sided Type I error = 2.5%
0.3333	0.3333	0.3333	0.96	0.87	0.79	0.873	0.83	0.7	0.66	0.73	98%
0.2	0.2	0.6	0.96	0.87	0.79	0.84	0.83	0.7	0.66	0.702	96%
0.2	0.6	0.2	0.96	0.87	0.79	0.872	0.83	0.7	0.66	0.718	99%
0.6	0.2	0.2	0.96	0.87	0.79	0.908	0.83	0.7	0.66	0.77	96%
0.3	0.3	0.4	0.96	0.87	0.79	0.865	0.83	0.7	0.66	0.723	97%
0.3	0.4	0.3	0.96	0.87	0.79	0.873	0.83	0.7	0.66	0.727	99%
0.4	0.3	0.3	0.96	0.87	0.79	0.882	0.83	0.7	0.66	0.74	98%
0.4	0.4	0.2	0.96	0.87	0.79	0.89	0.83	0.7	0.66	0.744	99%
0.4	0.2	0.4	0.96	0.87	0.79	0.874	0.83	0.7	0.66	0.736	98%
0.2	0.4	0.4	0.96	0.87	0.79	0.856	0.83	0.7	0.66	0.71	98%

Primary Statistical Analysis: The primary statistical analysis will be conducted in the FAS subjects overall and in the SARS-CoV-2 negative subgroup. The primary statistical comparison will use a one-sample Z-test comparing the proportion of subjects with primary patency to the PG using a one-sided $\alpha = 0.025$ equivalent to a z-score of 1.96. The variation in the proportion will be estimated using the disease-specific performance goals themselves, i.e. under the null, rather than use the estimated patency rates, i.e. under the alternative.

The estimates that will be observed for primary patency in each disease etiology are noted as follows:

$\hat{p}_{p_pat_NT}$ = The primary patency observed in the NT subjects.
 $\hat{p}_{p_pat_AT}$ = The primary patency observed in the AT subjects.
 $\hat{p}_{p_pat_CPT}$ = The primary patency observed in the CPT subjects.

The percent of subjects in the FAS with each disease etiology are noted as follows:

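### Read literally, the NT and CPT definitions overlap, so an unadjudicated label sets whether a subject adds 0.83 or 0.66 to the primary efficacy goal

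*Combined protocol and SAP*

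**What the plan says.** Section 9.3.1 has the investigator place each subject in one of three groups.

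- **NT:** "Symptomatic subjects with iliofemoral venous obstruction and no history of DVT". There is no limit on symptom duration.
- **Acute thrombotic (AT):** a first ipsilateral DVT no more than 14 days old. Lesions with a chronic component are moved to CPT.
- **CPT, first bullet:** "Total occlusion or stenosis of iliofemoral segments requiring stent placement with onset of symptoms more than 14 days ago". A separate second bullet covers any obstruction with an ipsilateral DVT in the past 2 years. Among the CPT bullets, DVT history appears only there.

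One exception moves subjects from NT to CPT: a complete occlusion that "extends into the EIV or CFV without involvement of iliac veins".

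The final class is recorded at the index procedure (section 13.1.3). Sections 21.7.2 and 21.9 describe the events committee and the core laboratories, and neither is given the task of confirming disease state.

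The label feeds the primary efficacy test in section 19.11: "The disease state PGs are .83, .70 and .66 for nonthrombotic, acute thrombotic and chronic postthrombotic subjects respectively". The study goal is their weighted average, "where the weights are the proportion of subjects in each disease state in the ITT sample". Section 19.5 fixes that goal in an administrative report after enrollment and before the efficacy analyses.

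**The concern.** The first CPT bullet is a condition on symptom duration and anatomy, not on cause. An ordinary compression subject with no DVT and months of symptoms satisfies it and also satisfies NT, and no general rule says which group takes precedence.

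Two smaller faults sit in the same section:

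- The EIV branch of the NT exception contradicts itself, because the external iliac vein is an iliac vein. The CFV branch does not.
- A subject with a DVT more than 2 years ago and symptom onset within 14 days may fit no group. The DVT history rules out NT. An earlier ipsilateral DVT means that the new event is not a first episode, as AT requires. Neither CPT bullet is met.

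The trial is single-arm, so the performance goal is the only comparator. Labelling a true NT subject CPT lowers that comparator. If the subject's real chance of patency is that of an NT subject, the observed proportion does not fall to match, and the test becomes easier to pass. The same label also defines the 20% minimum per group, the efficacy pooling strata (section 19.6) and the etiology summaries (section 19.12).

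**Working it through.** **Inputs (sections 19.3 and 19.11).** Goals 0.83 / 0.70 / 0.66 for NT / AT / CPT; evaluable N = 128; rejection at one-sided 0.025, "equivalent to a z-score of 1.96"; variance rule: "The variation in the proportion will be estimated using the disease-specific performance goals themselves, i.e. under the null"; for power, "assumed primary patency at 12 months equal to .96, .87, .79".

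**Method.** If the FAS and ITT shares are equal, the weighted patency is the total number patent divided by 128. With labelled counts n_i,

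PG = Σ n_i·PG_i / 128, and var = Σ n_i·PG_i(1 − PG_i) / 128².

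The test rejects when (X/128 − PG)/√var > 1.96. X is a sum of three independent binomials, so the probabilities are exact by convolution.

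**The plan's own figure.** Exact power over the ten tabled mixes is 97.2–99.5%, against the stated 96–99%. Nine rows agree within 2 points. The 0.6/0.2/0.2 row is stated as 96% and computes to 99.5%; that is a separate matter and does not enter what follows.

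**Shift in the goal.** 0.10 × (0.83 − 0.66) = 0.017. For 13 of 128 subjects it is 13/128 × 0.17 = 0.0173.

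**Worked case, equal mix (43/43/42), each true rate at its own goal.**

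- Correct labels: PG = (35.69 + 30.10 + 27.72)/128 = 0.7305. Var = (43×0.1411 + 43×0.21 + 42×0.2244)/128² = 24.522/16384, so the SE is 0.0387. The cut-off is 0.7305 + 1.96×0.0387 = 0.806, or 104 patent subjects. Type I error is 1.9%.
- Thirteen NT subjects labelled CPT (30/43/55): PG = (24.90 + 30.10 + 36.30)/128 = 0.7133. Var = (30×0.1411 + 43×0.21 + 55×0.2244)/128² = 25.605/16384, so the SE is 0.0395. The cut-off is 0.791, or 102 patent subjects. The true distribution of X has not changed, and type I error is 5.0%.

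**Across the ten mixes (one-sided, nominal 2.5%).**

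| Scenario | Type I error |
|---|---|
| Correct labels | 1.9–2.8% |
| 6 NT subjects labelled CPT, true rate 0.83 | 2.8–4.3% |
| 13 labelled CPT, true rate 0.83 | 5.0–6.8% |
| 20 labelled CPT, true rate 0.83 | 7.7–10.2% |
| 13 labelled CPT, true rate 0.745 (midway) | about 3.2–4.5% |
| 13 labelled CPT, true rate 0.66 | 2.0–2.8% (no inflation) |
| 13 CPT subjects labelled NT | 0.6–1.0% (conservative) |

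The 13-subject range covers two readings of the power table: its mix as the true mix (5.0–6.7%) and as the labelled mix (5.1–6.8%).

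**Scale of the assumption.** Thirteen subjects are 13/77 = 17% of NT subjects when NT is 60% of the sample, 13/43 = 30% at equal thirds, and 13/26 = 50% when NT is 20%. In that last case the labelled NT share would be 13/128 = 10%, below the plan's 20% floor, so that end can arise only if the tabled mix is the labelled one. Moving only 10% of NT subjects (3 to 8 people) gives 2.6–4.2%.

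**Hochberg.** Applying the two-population rule to four of the mixes, with 0–40% of subjects SARS-CoV-2 positive and 13 moved, familywise error is 4.1–6.7% by simulation, against 1.6–2.8% with correct labels.

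**The case against.** The strongest reply is that the section makes its purpose clear. It groups subjects by etiology, the group is called postthrombotic, NT is the only group defined by absence of DVT, and section 4.1 contrasts nonthrombotic with postthrombotic disease. The limit of more than 14 days then reads as the counterpart of AT's limit of 14 days or less. This stands as evidence of intent, and most investigators may read it that way. It does not remove the overlap, because the first bullet does not state the condition. Where the section wants a precedence rule it writes one, and none covers this case.

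Four stronger readings are tempting and are not supported:

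- **That the efficacy test has a type I error of 5–7%.** No misclassification rate or direction is given. Thirteen subjects all moving from NT to CPT, each with a true rate of 0.83, is an assumption. Thirteen errors in each direction leave the error at 1.9–2.8%.
- **That labels could be changed to suit results.** The final class is recorded at the index procedure and the goal is fixed before the efficacy analyses. Outcome-driven relabelling is not alleged.
- **That the whole NT exception is impossible.** Isolated CFV occlusion satisfies it, and sending such subjects to CPT is an explicit rule. Only the EIV branch fails.
- **That subjects commonly fall outside every group.** The gap needs an old DVT together with recent onset, and AT's chronic-component rule may absorb some of these cases.

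**Conclusion.** The point holds as an ambiguity in a definition that sets the primary efficacy threshold. By the text, a subject with no DVT history and symptoms for more than 14 days meets both NT and CPT, the investigator chooses, and the choice moves that subject's contribution to the goal by 0.17. What is certain is the shift of 1.7 points per 10% of the sample.

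The type I error figures illustrate sensitivity only. They rest on N = 128, equal FAS and ITT shares, true rates exactly at the class goals, errors in one direction, and moved subjects who truly have the NT null rate. They concern the efficacy endpoint alone; study success also requires safety. The first CPT bullet pulls a literal reader in the anti-conservative direction, and nothing in the plan bounds how many subjects move. The repair should be made, but the documents do not show that the test is invalid.

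**What to change.** Before the administrative report that fixes the goal:

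1. Make the three groups mutually exclusive and exhaustive for the analysis. State that symptoms over 14 days do not by themselves qualify a subject as CPT without documented prior ipsilateral DVT or post-thrombotic change on the index venogram or IVUS.
2. Reconcile the EIV/CFV clause, and assign subjects with a DVT more than 2 years ago and recent onset to a group.
3. Add a sensitivity analysis that moves CPT-labelled subjects with neither DVT history nor post-thrombotic imaging change to NT (goal 0.83) and recomputes the goal, weights and variance. Leave AT subjects unchanged.
4. Optionally, have the core laboratory confirm the imaging component from index images that it already receives. Etiology also rests on history, which images do not show.

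Section 12.3 ties minimum anticoagulation duration to nonthrombotic versus thrombotic status. That passage must be reconciled with the revised definitions; no change to the clinical rule is proposed here.

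The cost is protocol and SAP wording, one extra analysis and, if item 4 is adopted, one extra core laboratory field. The goal may come out slightly higher.
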